9.7.3.3 Statistical Methods for Analysis of Effectiveness Variables

The simple percentage of patients achieving SVR12 will be calculated and an exact two-sided 95% confidence interval (CI) of the percentage will be computed based on the Clopper-Pearson method.

Corresponding methods will be used for other response rates (EoT response rate, relapse rate, viral breakthrough). The relapse rates will be estimated in patients of the CP analysis groups with EoT response and sufficient HCV RNA measurements post-treatment. Viral breakthrough rates will be estimated in all patients of the CP analysis groups, who have at least one undetectable HCV RNA measurement on-treatment and at least one on-treatment or EoT measurement thereafter.

Univariate and multiple logistic regression (MLR) methods will be used to investigate the impact of the following explanatory covariates on SVR12:

- Key demographic information
- Mode of CHC infection
- HCV RNA level at baseline
- Most recent stage of liver fibrosis
- HCV genotype and subtype (if available)
- Type of treating institute
- Liver and/or CHC related co-morbidities
- Key clinical chemistry and hematology laboratory variables at baseline
- In treatment experienced patients only:
 - Most recent prior treatment for CHC
 - Outcome of most recent prior CHC treatment

Further details and additional covariates will be specified in the SAP.

These analyses will be of exploratory nature, data driven, and will be repeatedly performed for various CP Analysis Groups, since not each covariate might be

predictive in each patient group. Furthermore, the fact that treatment regimens will differ in the various patient groups has to be taken into account, when selecting the patient groups for each MLR analysis. Backward selection procedures will be applied to generate the final MLR models which consider only covariates in the selection procedure with a p-value <0.25 in the corresponding univariate logistic regression analysis. A p-value <0.05 will be used for the covariates to stay in the model in a backward elimination step. Logistic regression methods will also be used to investigate the impact of treatment adherence on SVR12.

9.7.4 Clinical Laboratory Data

All reported clinical laboratory test results will be assigned to one of the time points using the time windows specified in the table below.

Table 4 - Analysis Time Windows

Phase	Time point	Time Window
Pre-Treatment	Baseline	Last value prior to start of study treatment (i.e. ≤study day 1)
Treatment Weeks	4 (day 29)	Study day during treatment period (Study day 1 = first treatment day) 15 - 42
	8 (day 57)	43 - 70
	12 (day 85)	71 - 98
	16 (day 113)	99 - 126
EoT	Actual EoT	Study day of last dose (28 days prior to EoT - 14 days post EoT)
Post Treatment	4 weeks (day 29 post EoT)	15 – 56 post EoT
	12 weeks (day 85 post EoT)	57 – 112 post EoT
	24 weeks (day 169 post EoT)	141 – 196 post EoT

Mean changes from baseline to each post-baseline visit will be summarized descriptively.

Laboratory data values collected during the treatment period will be categorized as low, normal, or high based on reference ranges used in this study. The number and percent of patients who experience post-baseline shifts during treatment in clinical laboratory values from low/normal to high and high/normal to low based on the reference range will be summarized.

Confidential Information

No use or disclose outside AbbVie is permitted without prior written authorization from AbbVie

Additional details of the analyses of clinical laboratory data will be specified in the SAP.

9.7.5 PRO Questionnaires

The EQ-5D-5L is a health state utility instrument that evaluates preference for health status (utility). The EQ-5D-5L comprises 5 dimensions (mobility, self-care, usual activities, pain/discomfort, anxiety/depression) each of which are rated on 5 levels of severity (1: indicating no problem, 2: indicating slight problems, 3: indicating moderate problems, 4: indicating severe problems, 5: indicating extreme problems), and a separate VAS.

Patients' responses to the EQ-5D-5L will be combined into a unique health state using a 5-digit code with one digit from each of the 5 dimensions representing the level of severity. These EQ-5D-5L states will be converted into a single preference-weighted health utility index score by applying country-specific weights (if available) or US weights (if not available).

No imputation will be performed for missing items, and in case of missing items no index score will be calculated.

A summary table will show descriptive statistics (n, mean, median, SD, minimum and maximum) of the index score values and for the VAS values for baseline and the post-baseline time points, as well as changes from baseline both for the index score values and for the VAS values. In addition analysis of covariance (ANCOVA) will be applied to investigate the effect of the different ABBVIE REGIMENS (\pm RBV and duration) on EQ-5D-5L endpoints using the corresponding EQ-5D-5L baseline values as covariates.

Assessments of work productivity and activity impairment as assessed by the WPAI Hep C v2.0 will be evaluated according to the WPAI-SHP scoring manual. The WPAI yields four types of scores, the results of which will be presented as percentage of impairment from 0 to 100. Higher percentages indicate greater impairment:

1. % absenteeism: percentage of work time missed due to hepatitis C
2. % presenteeism: percentage of impairment while working due to hepatitis C
3. % TWP: percentage of overall work impairment due to hepatitis C
4. % TAI: percentage of general (non-work) activity impairment due to hepatitis C

The WPAI Hep C v2.0 consists of 6 questions aimed at the following targets:

- Q1. currently employed (yes, no)
- Q2. hours missed due to hepatitis C in the last seven days
- Q3. hours missed due to other reasons in the last seven days
- Q4. hours actually worked in the last seven days

Confidential Information

No use or disclose outside AbbVie is permitted without prior written authorization from AbbVie

Q5.degree hepatitis C affected productivity while working
Q6.degree hepatitis C affected regular activities

The four scores will be derived as follows:

1. % absenteeism: $100 * Q2 / (Q2 + Q4)$
2. % presenteeism: $100 * Q5 / 10$
3. % TWP: $100 * \{Q2 / (Q2 + Q4) + [Q4 / (Q2 + Q4)] * Q5 / 10\}$
4. % TAI: $100 * Q6 / 10$

A score will be set to missing if one or more of the items Q1-Q6 that are needed for the calculation of the score are missing. No imputation will be performed for missing items.

The summary table will present the absolute and relative frequencies of employed and unemployed patients and descriptive statistics for the four scores. Further details of the analysis will be specified in the SAP.

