9.4.1.3 Post-Treatment Documentation

Follow-up visits are scheduled by the physician per routine clinical practice. Likewise treatment, procedures and diagnostic methods will follow physicians' routine clinical practice.

The following will be documented:

- Laboratory data

- Key clinical chemistry

- ALT
 - AST

- Remarks

- including ULN
including ULN,
APRI and FIB-4, will be calculated

- γ -GT
 - Total bilirubin
 - Albumin
 - Creatinine

- creatinine clearance will be calculated

- Key hematology

- Hb
 - Platelets
 - Prothrombin time

- or INR

- Virology

- HCV RNA

- quantitative/ qualitative HCV RNA PCR test, see 9.4.1.4

- HIV-infected patients only

- CD 4 count
 - HIV RNA

- most recent assessment
in copies/mL

- Tolerability (sAEs, see 0) and pregnancies (see 0)
- Patient questionnaires see 9.4.1.6

Confidential Information

No use or disclose outside AbbVie is permitted without prior written authorization from AbbVie

Table 2 - Data Documentation Schedule

Assessment/ Procedure (only available data to be collected; no diagnostic or monitoring procedures to be applied to the patients apart from those of routine clinical practice)	Baseline	Treatment Period			Post-treatment (PT) Period		
		On-treatment visits	Mid treatment visit for pts receiving 24 weeks of therapy	EoT ^b	Early PT visit	SVR 12 visit	SVR 24 visit
Patient authorization	X ^a						
Demographic information	X						
IL28B	X						
Relevant CHC disease characteristics	X						
Liver fibrosis stage	X						
CHC treatment history	X						
HCV genotype and subtype	X						
HCV RNA samples	X	X	X	X	X	X	X
Clinical chemistry and hematology	X	X	X	X	X	X	X
ABBVIE REGIMEN initiation documentation	X						
ABBVIE REGIMEN adherence		X	X	X			
Concomitant medication	X	X	X	X			
Relevant medical history, co-morbidities	X						
sAE, AE and pregnancy reporting	X	X	X	X	X ^c	X ^d	X ^d
For patients receiving RBV: Evidence, in accordance with local label, that female patient or female partner of male patient is not pregnant	X						
Patient questionnaires – WPAI, EQ5D-5L	X			X		X	X

Abbreviations: EoT = End of Treatment (at Week 12 or 24 or at premature discontinuation), PT = Post-Treatment

- a Written patient authorization must be obtained before any data documentation in the eCRF
- b Patients who prematurely discontinue should return to the site to document EoT data
- c Tolerability documentation until PT week 4
- d Pregnancy reporting for patients treated with DAA plus RBV

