No data will be imputed for any effectiveness or safety analyses except for the analyses of the HCV RNA endpoints. When there is no HCV RNA value in a visit time window post-baseline, but prior to EoT, the closest values before and after the window, regardless of the value chosen for the subsequent and preceding window, will be used for the flanking imputation described below. If a patient has a missing HCV RNA value at a post-baseline visit prior to EoT but has undetectable HCV RNA (with LLoD ≤ 50 IU/mL) or unquantifiable, but detectable HCV RNA levels (with LLoQ ≤ 50 IU/mL) at both the preceding and succeeding measurements, the HCV RNA level will be considered undetectable or unquantifiable, respectively, at this visit for this patient. In addition, if a patient has an unquantifiable HCV RNA level at the preceding measurement and an undetectable HCV RNA level at the succeeding measurement, or vice versa, the HCV RNA level will be imputed as unquantifiable at this visit for this patient. For virological response at EoT a corresponding backward imputation approach will be applied. This means if HCV RNA is missing at EoT, then unquantifiable or undetectable will be assumed for EoT, if the succeeding HCV RNA value is undetectable or unquantifiable. For SVR12 the single last available HCV RNA measurement ≥ 70 days post-treatment will be used. Subsequent to this flanking and backward imputation, if the HCV RNA value remains missing at a specific time point, then the patients will be considered as virological failure at this time point (i.e. not undetectable or unquantifiable).

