# 4.2.3 Handling of missing data

No data will be imputed for any effectiveness or safety analyses except for the analyses of the HCV RNA endpoints and certain PRO endpoints. The discussion of missing data imputation for the PRO endpoints is included in section 4.2.7.2.3.

HCV RNA values will be selected for an RVR, EOTR and SVR analysis based on visit windows as defined in Table 3. When there is no HCV RNA value in a visit window based on defined visit windows, the closest values before and after the window, regardless of the value chosen for the subsequent and preceding window, will be used for the flanking imputation described below. For analysis of RVR, EOT and SVR, if a subject has a missing HCV RNA value at a post-Day 1 visit but with undetectable or unquantifiable (≤50 IU/mL) HCV RNA levels at both the preceding value and succeeding value, the HCV RNA level will be considered undetectable or unquantifiable,

respectively, at this visit for this subject. In addition, if a subject has an unquantifiable HCV RNA level at the preceding value and an undetectable HCV RNA level at the succeeding value, or vice versa, the HCV RNA level will be imputed as unquantifiable at this visit for this subject.

For analyses of RVR, subjects still missing a value for the visit after flanking imputation will be imputed as a failure. For EoTR and SVR analysis, if there is no value in the appropriate window after flanking imputation but there is an HCV RNA value after the window, then it will be imputed into the EoTR or SVR window respectively. Subsequent to this flanking imputation, if a subject is missing a value for the visit window associated with the analysis, the subject will be imputed as a visit failure (i.e., not undetectable or unquantifiable).

If a subject starts another treatment for HCV, then all HCV RNA values for this subject measured on or after the start date of the new HCV treatment will be excluded from analyses. The subject will be considered a failure for summaries of viral response at all time points after the start of the new HCV treatment.

Due to the non-interventional nature of this study several different methods for determination of the HCV RNA value can be applied. For the purpose of the statistical analysis, a HCV RNA measurement is considered ≤50 IU/mL.

- if a PCR test was used

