### Assessment of general quality of life - EQ-5D-5L

The EQ-5D-5L is a health state utility instrument that evaluates preference for health status

(utility). The 5 items in the EQ-5D-5L comprise 5 dimensions (mobility, self-care, usual activities, pain/discomfort, and anxiety/depression) each of which are rated on 5 levels of severity (1: indicating no problem, 2: indicating slight problems, 3: indicating moderate problems, 4: indicating severe problems, 5: indicating extreme problems), and a separate VAS.

Patients' responses to the EQ-5D-5L will be combined into a unique health state using a 5-digit code with one digit from each of the 5 dimensions representing the level of severity. These EQ-5D-5L states will be converted into a single preference-weighted health utility index score by applying country-specific weights (if available) or US weights (if not available). (3)

No imputation will be performed for missing items, and in case of missing items no index score will be calculated.

A summary table will show descriptive statistics (n, mean, median, SD, minimum and maximum) of the index score values and for the VAS values for baseline and the post-baseline time points, as well as changes from baseline, by cirrhosis status and treatment regimen. In addition, analysis of covariance (ANCOVA) will be applied to investigate the effect of the different ABBVIE REGIMENS (± RBV) by cirrhosis status on EQ-5D-5L endpoints at the post-baseline time points using the corresponding EQ-5D-5L baseline values as covariates.

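### The EQ-5D-5L ANCOVA at each post-baseline time point has no rule for a missing whole questionnaire and ignores scores already held; the resulting bias is modest and conditional, and cheap to remove

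*Protocol*

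**What the plan says.** Secondary objective 7 is to document the regimen's effect on PROs and work productivity. EQ-5D-5L is scheduled at baseline, EoT, and 12 and 24 weeks after EoT. The schedule (protocol Table 2, repeated in the SAP) carries the qualifier "only available data to be collected".

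**Model.** Protocol 9.7.5 applies ANCOVA "on EQ-5D-5L endpoints using the corresponding EQ-5D-5L baseline values as covariates" and names ribavirin use and duration as the regimen factors. SAP 4.2.7.2.2 intends to "investigate the effect of the different ABBVIE REGIMENS (± RBV) by cirrhosis status", and fits the ANCOVA "on EQ-5D-5L endpoints at the post-baseline time points using the corresponding EQ-5D-5L baseline values as covariates". Neither document names a visit term, a within-patient covariance, a missingness assumption or a sensitivity analysis for EQ-5D-5L.

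**Missing data.** Four statements bear on it:

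- Protocol 9.7.1: "No data will be imputed for any effectiveness or safety analyses except for the analyses of the HCV RNA endpoints".
- SAP 4.2.3 widens that exception: "No data will be imputed for any effectiveness or safety analyses except for the analyses of the HCV RNA endpoints and certain PRO endpoints". SAP 4.1.2 makes a similar exception for PRO questionnaires where applicable.
- SAP 4.2.3 then sends the reader elsewhere: "The discussion of missing data imputation for the PRO endpoints is included in section 4.2.7.2.3". In the SAP, 4.2.7.2.2 is followed directly by 4.2.8.
- SAP 4.2.7.2.2 (likewise protocol 9.7.5): "No imputation will be performed for missing items, and in case of missing items no index score will be calculated". This concerns items left blank within a questionnaire, not a questionnaire that was never returned.

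**The concern.** An ANCOVA at a given time point has no row for a patient with no score at that time point. A patient with EoT and 12-week scores but no 24-week score therefore contributes nothing at 24 weeks, and the table of changes from baseline is restricted in the same way. If patients who felt worse at EoT or 12 weeks return fewer later questionnaires, those who remain look better than the cohort. Baseline adjustment does not repair this, because the missingness follows scores recorded after baseline.

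At stake are the later-visit results for objective 7: the mean change and, under further conditions, the comparison with and without ribavirin. Those conditions are plausible here. Protocol 7.1 attributes many adverse events and laboratory abnormalities to ribavirin, and the regimen is chosen by the physician according to patient characteristics. EoT scores or return rates could therefore differ by regimen.

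**Working it through.** **The plan's own figure.** The only study-size figures are exact confidence-interval widths for SVR12. They reproduce: 400 × 0.90 = 360 and 400 × 0.95 = 380 evaluable patients, with widths of 6.47 and 6.29 points at a 90% rate (stated as 6.5 and 6.3). They say nothing about EQ-5D-5L, for which the documents give no SD, correlation, effect or missing rate.

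**Assumed inputs (none from the documents).** Normal scores with SD σ = 0.20; 380 patients, 190 with and 190 without ribavirin; no cirrhosis strata; correlations of 0.7 between 12 and 24 weeks and 0.5 between baseline and each of these; odds of a missing 24-week score doubling per SD lower 12-week score; no regimen effect on any score.

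**Step 1: selection.** Let z be the standardised 12-week score and p(z) = 1/(1 + exp(−(a − z ln 2))) the probability of a missing 24-week score, with a set so that p averages to the missing fraction m. The mean of z among those still observed is d(m) = E[z(1 − p)]/(1 − m). Numerical integration gives d = 0.098, 0.129, 0.190 and 0.251 for m = 15, 20, 30 and 40%.

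**Step 2: mean change at 24 weeks.** Bias = σ × (r(12,24) − r(0,12)) × d.

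- 20% missing: 0.20 × (0.7 − 0.5) × 0.129 = 0.0052
- 30% missing: 0.20 × (0.7 − 0.5) × 0.190 = 0.0076

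Simulations with similar inputs gave 0.004 to 0.007. If all visits are equally correlated, the bracket is zero and this bias vanishes. The 24-week mean score itself would be too high by 0.20 × 0.7 × 0.129 = 0.018 (20%) or 0.20 × 0.7 × 0.190 = 0.027 (30%).

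**Step 3: regimen contrast at 24 weeks, baseline-adjusted.** With adjustment slope r(0,24) = 0.5, bias ≈ σ × (r(12,24) − r(0,24) × r(0,12)) × (d with RBV − d without RBV), and the first bracket is 0.7 − 0.25 = 0.45.

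- 30% missing against 15%: 0.20 × 0.45 × (0.190 − 0.098) = 0.008, about 0.4 of a simulated SE of 0.020
- 40% against 15%: 0.20 × 0.45 × (0.251 − 0.098) = 0.014, about 0.65 of an SE of 0.021
- 30% against 30%: d is equal in both groups, so the bias is 0

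**Step 4: other mechanisms.** A separate simulation let missingness at 24 weeks depend on the baseline or EoT score. It used n = 380, SD 0.20, correlation 0.5 or 0.7, 10 to 30% missing, logit slope 1.5 per SD, a true 24-week effect of 0, and 1,500 runs per setting.

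| Missingness at 24 weeks | Bias of the ANCOVA contrast |
|---|---|
| follows baseline only | within 0.001 of 0 |
| follows EoT, same rule, no regimen effect at EoT | within 0.001 of 0 |
| follows EoT, same rule, regimen effect at EoT of −0.05 | 0.001 to 0.003 |
| same, regimen effect at EoT of −0.10 | 0.003 to 0.006 (at most about 0.3 SE) |
| follows EoT in one regimen only | 0.006 to 0.019 in size (about 0.4 to 0.9 SE) |

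Complete-case SEs were 0.015 to 0.022 and Monte Carlo error about 0.0005. A likelihood-type estimator that also uses the post-baseline scores already held stayed within 0.001 of zero in every setting of Steps 3 and 4.

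**The case against.** **The bias is not general.** A reader might infer that the contrast is biased whenever missingness follows earlier quality of life. That is too strong. Baseline is an earlier score and is in the model, and a common rule acting on unshifted post-baseline scores leaves the contrast unbiased (Steps 3 and 4). Nor can one say that the effect would be overstated: the direction depends on who fails to respond. This objection stands and sets the limits of the claim.

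**The documents do not say complete-case.** A reader might also infer that the plan imputes nothing and fits separate models by visit. Neither is stated. Visit-wise fitting is the natural reading of SAP 4.2.7.2.2, not its wording. The SAP allows for some PRO imputation, and the no-imputation sentences concern items. But the section that should give the method is not in the SAP, so nothing there covers a missing questionnaire.

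**The contrast is weak anyway.** Regimen follows genotype and cirrhosis by physician choice. The core-population exclusions leave dasabuvir-free treatment without ribavirin essentially empty, and with ribavirin essentially genotype 4. Splitting by cirrhosis enlarges the SE and lowers the bias relative to it. The analysis is secondary, in a study described as descriptive and exploratory. All this stands and keeps the point minor.

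**Partly covered already.** The tables report n per time point by regimen and cirrhosis status, and protocol 9.9 lists missing data as a limitation. Counts show the loss but do not use the earlier scores.

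**Conclusion.** The point holds in limited form. The only specified EQ-5D-5L model is a baseline-adjusted ANCOVA at the post-baseline time points, with no stated method for a missing whole questionnaire. On the natural reading, known EoT and 12-week scores go unused for patients missing later ones.

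The mean change can be biased when missingness depends on those scores: about 0.004 to 0.008 index units, against an assumed gain of 0.05, and zero if all visits are equally correlated. The regimen contrast is biased only if the post-baseline scores or the missingness rule also differ by regimen: from 0 to about 0.02, below one SE throughout. Every size rests on assumed SD, correlations, group sizes and missing rates. SVR12, the primary endpoint, is unaffected. This is a worthwhile improvement rather than a defect that undermines the study.

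**What to change.** Amend SAP 4.2.7.2.2 and protocol 9.7.5 as follows:

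- For the index and the VAS, replace the ANCOVA at the post-baseline time points by one likelihood-based repeated-measures model over EoT, 12 and 24 weeks. Include regimen, visit, regimen × visit, baseline and baseline × visit, with unstructured covariance and a named simpler structure if it does not converge.
- Keep cirrhosis status, as a stratum or as a term with its regimen interaction, and planned duration where protocol 9.7.5 requires it.
- Report adjusted means and regimen contrasts with 95% confidence intervals at each visit, and questionnaires returned by regimen and visit.
- State the missing-data assumption. Either supply section 4.2.7.2.3 or delete the reference to it and align SAP 4.1.2 and 4.2.3.

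The cost is SAP and protocol wording and one modelling procedure on data already collected. There are limits. The model assumes that missingness depends on observed scores. It may be unstable in sparse regimen-by-cirrhosis cells. With baseline as a covariate it still omits patients without a baseline score. It does not remove the confounding of regimen with genotype and cirrhosis.
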